6.2. Adjustments for Covariates

The MMRM models will include the fixed, categorical effects of treatment, country, month, and treatment-by-month interaction, as well as the continuous, fixed covariates of baseline value and baseline-by-month interaction. The baseline value and baseline-by-month interaction are included to account for the differential influence over time that the baseline value has on the post-baseline values. Country will be excluded from MMRM models for safety measures.

When an ANCOVA model is used to analyze a continuous efficacy at the LOCF endpoint, the model will contain the main effects of treatment, country, and appropriate baseline value as a covariate. When an ANCOVA model is used to analyze a continuous safety variable, the country will be removed from the model.

The GLIMMIX models for the repeated binary outcomes will include the fixed, categorical effects of treatment, month, and treatment-by-month interaction, as well as the continuous, fixed covariate of baseline value. Country and the baseline value-by-month interaction will be excluded from the model in order to increase the likelihood of convergence.

When a logistic regression is used to analyze a binary variable, the model will include the main effect of treatment, country (if appropriate), and appropriate baseline value as a covariate. Country may be excluded from the model in case of non-convergence.

With the exception of efficacy analyses on migraine headache days or categorical analysis of response rate (such as 50% response rate) derived from migraine headache days where the continuous value of baseline migraine headache days will be used as covariate, all other efficacy analyses will include baseline number of migraine headache days category (<8 vs ≥ 8) as a covariate in the MMRM, ANCOVA, GLIMMIX and logistic regression model. Specifically, for time to event analysis of 50% response (such as Time to first 50% response in double-blind treatment phase and Time to first loss of 50% response in post-treatment phase), stratified log rank test will be used with the baseline number of migraine headache days category (<8 vs ≥ 8) as one of the covariates.

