5.3. Method of Assignment to Treatment

Following a prospective baseline (30 to 40 days) period, eligible patients will be randomized in a 1:1 ratio to receive placebo or 120 mg/month of galcanezumab (with a 240 mg loading dose at the first injection [administered as 2 injections of 120 mg at Visit 3]), respectively, and will begin a 3-month double-blind treatment phase. Patients who complete the double-blind period may enter a 3-month open-label extension phase during which all patients will receive galcanezumab 120 mg/month. At Visit 7, patients originally assigned to placebo will receive an initial loading dose of 240 mg galcanezumab; patients originally assigned to galcanezumab will continue the dose of 120 mg but will receive 2 injections (1 injection of 120 mg galcanezumab and 1 injection of placebo) to maintain blinding. At Visit 8 and Visit 9 of the open-label phase, all patients will receive a 120 mg dose of galcanezumab. All patients will be followed for a 4-month, post-treatment phase during which no study medication will be administered.

Patients who meet all criteria for enrollment will be randomized to double-blind treatment at Visit 3. Assignment to treatment groups will be determined by a computer-generated random sequence using an interactive web-response system (IWRS). The IWRS will be used to assign double-blind investigational product to each patient. Site personnel will confirm that they have located the correctly assigned package by entering the confirmation number found on the package into the IWRS.

To achieve between-group comparability, the randomization will be stratified by country and baseline migraine frequency (<8 MHDs versus \geq 8 MHDs). To ensure an appropriate balance of patients with low- and high-frequency MHDs, the sponsor will stop enrollment of low-frequency patients if the number exceeds an estimated 292.

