6.4. Multiple Comparisons/Multiplicity

In order to provide strong control of the Type I error, the key secondary analyses will be tested using a gated testing approach at a 2-sided alpha level of 0.05. If the null hypothesis is rejected for the primary endpoint, key secondary endpoints will be sequentially tested following the gatekeeping hierarchy as shown in [Figure CGAX. 6.1](#).

Following the primary objective, the sequential procedure for key secondary objectives starts with the comparison between treatment groups in the 50% response rate. If that null hypothesis is rejected, then the next comparison in the sequence will be tested, following this same pattern until all hypotheses are tested or until the null hypothesis is accepted for an endpoint, at which point, any further testing would stop for the key secondary objectives.

Abbreviations: MHD = the number of monthly migraine headache days; MSQ RR = Migraine Specific Quality of Life Questionnaire Role Function-Restrictive domain; response = response rate. See Section 5.4 for full definitions of endpoints. Note: All testing will be conducted at a 2-sided alpha of 0.05.

Figure CGAX. 6.1 Gatekeeping sequence for testing of primary and key secondary endpoints.

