To assess the robustness of the MMRM results to deviations from normality assumption, a sensitivity analysis for raw number of migraine headache days (total number of migraine headache days for each interval without normalization to 30-day period) will be conducted with a repeated measures negative binomial regression model fitted with SAS PROC GLIMMIX. The model will include treatment, country, month, and treatment-by-month interaction, as well as the continuous fixed covariates of baseline number of monthly migraine headache days and baseline-by-month interaction, log (number of compliant days within each month/30) as the offset in the model. In case of non-convergence, country and/or baseline-by-month interaction may be excluded from the model. Directional consistency of treatment effects from this model and the primary analysis MMRM model as specified in Section 6.10.1 will be examined.

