6.10.3. Secondary and Exploratory Efficacy Analyses

Key secondary efficacy measures will be tested in the order as specified in Section 6.4.

Table CGAX. 6.2 summarizes all the planned secondary and exploratory efficacy analyses for SP III, SP III/IV, and SP III/IV/V, not including analyses for health outcome measures. Additional statistical analysis details are also provided below.

Continuous Efficacy Measures

For the continuous secondary efficacy measures, the change from baseline will be estimated from MMRM as described for analysis for primary outcome or ANCOVA as described in Section 6.1.

For continuous secondary efficacy measures where the objective is to assess overall mean change during 3-month double-blind treatment phase, the endpoint for galcanezumab compared with placebo will be estimated as the treatment main effect from the MMRM analysis assessing the average treatment effect across Months 1, 2, and 3.

Binary Efficacy Measures

For the repeated binary efficacy measures such as responder indicators based on the number of migraine headache days, the visit-wise binary outcomes indicating whether patients meet X% response criteria will be analyzed using a categorical, pseudo-likelihood-based repeated measures analysis. This analysis will be implemented using the GLIMMIX procedure in SAS to compare treatments with covariates adjustment described in Section 6.2.

An unstructured covariance structure will be used to model the within-patient errors (denoted by TYPE=CHOL in the RANDOM statement). The Newton-Raphson method with ridging will be used for nonlinear optimization (denoted by including NLOPTIONS TECH=NRRIDG). The Kenward-Roger approximation will be used to estimate denominator degrees of freedom. If the model does not converge, the Fisher's scoring algorithm will be utilized by the SCORING option in SAS.

If the model still fails to converge, the model will be fit using covariance matrices in the following order specified by a decreasing number of covariance parameters until convergence is met:

- Heterogeneous Toeplitz,
- Heterogeneous autoregressive,
- Toeplitz, and
- Autoregressive.

If necessary, both fitting algorithms will be used in the pre-specified order before proceeding to the next covariance structure in the sequence.

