For models where the unstructured covariance matrix is not utilized, the sandwich estimator (Diggle et al. 1994) will be used to estimate the standard errors of the fixed effects parameters. The sandwich estimator is utilized by the EMPIRICAL option in SAS. When the sandwich estimator is utilized, the Kenward-Roger approximation for denominator degrees of freedom cannot be used. Instead, the denominator degrees of freedom will be partitioned into between-subject and within-subject portions by the DDFM=BETWITHIN option in SAS.

For the binary secondary efficacy measures where the objective is to assess proportion of patients with X% response during the 3-month double-blind treatment phase, the endpoint for galcanezumab compared with placebo will be estimated as the treatment main effect from the categorical MMRM analysis assessing the average response rate across Month 1, Month 2, and Month 3.

For visit wise indicators of 50% responders, the results of the statistical tests at each month in the double-blinded treatment phase from categorical MMRM analysis will be used to assess the onset of 50% sustained response for galcanezumab compared with placebo. In particular, if the gated secondary measure of 50% response rate is statistically significant, then the earliest month where the statistically significant improvement is observed and maintained for all the subsequent months during double-blinded treatment phase will be considered as the period that demonstrated the onset of 50% sustained response.

For binary secondary efficacy measures such as the proportion of patients who maintain 50% response criteria for all 3 months of double-blind treatment, as well as the proportion of patients who demonstrate 50% response for all 3 months in the open-label treatment period among patients previously treated with galcanezumab who met 50% response criteria at Month 3 in the

double-blind treatment period, treatment differences will be determined using logistic regression with covariate of treatment, country and continuous baseline value.

Measures Conditional on the Postbaseline Number of Migraine Headache Days >0

The following measures are conditional on the number of migraine headache days >0:

- Mean severity of remaining migraine headaches

Those measures will be analyzed using MMRM model, assuming that data are missing for months without migraine headache.

The number of weekly migraine headache days in Month 1

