If statistically significant improvement is observed at Month 1 and maintained for all the subsequent months during the double-blind treatment phase for the number of monthly migraine headache days, the number of weekly migraine headache days in Month 1 will be analyzed to identify the earliest week where the statistically significant improvement is observed and maintained for all the subsequent weeks in Month 1 for patients who have a monthly diary compliance rate greater than 50% for Month 1.

The number of weekly migraine headache days in Month 1 can be considered as ordinal data with possible values of 0, 1, 2, 3, 4, etc. and will be analyzed using an ordinal repeated measures model using the GLIMMIX procedure in SAS. In this model, a proportional odds model with cumulative logit link will be used, and a random intercept will be applied to the observations for each patient to account for repeated measures. The model will include the fixed, categorical effects of treatment, country, week, and treatment-by-week interaction, as well as the continuous, fixed covariate of weekly baseline number of migraine headache days and weekly baseline number of migraine headache days-by-week interaction. Log (number of compliant calendar days within each week/7) will be included as the offset in the model. For weekly diary compliance rate $\leq 50\%$, the number of weekly migraine headache days during that week will be considered missing.

The weekly baseline number of migraine headache days will be derived as (the monthly number of migraine headache days)/30*7.

Time to Event Measures

For the following time to event measures, a Kaplan-Meier curve of the time to event and treatment group comparison using stratified log-rank test stratifying for country, baseline MHD frequency category will be provided.

- Time to first 50% response in SP III for ITT population.
- Time to first loss of 50% response in SP V for patients who met 50% response criteria at their last injection interval and also entered SP V.

- Time to initiation of preventative treatment for migraine or probable migraine in SP V for patients who entered SP V and those who are not on concurrent preventive treatment group.

Distribution of Response Rate

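### SAP 6.2 leaves country, a randomisation factor, out of the response models behind three of the four key secondary tests, at some cost in power if response differs by country

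*SAP*

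**What the plan says.** SAP 5.3 and Protocol 7.2 make country a randomisation factor: "the randomization will be stratified by country and baseline migraine frequency" (below 8 versus 8 or more MHDs). SAP 6.2 then sets out the response models: "The GLIMMIX models for the repeated binary outcomes will include the fixed, categorical effects of treatment, month, and treatment-by-month interaction", plus the continuous baseline value. It adds: "Country and the baseline value-by-month interaction will be excluded from the model in order to increase the likelihood of convergence". The exclusion is made in advance and is not a fallback. SAP 6.10.3 applies the 6.2 covariates to the X% response endpoints.

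SAP 4 lists four key secondary endpoints: 50% response, MSQ Role Function-Restrictive, 75% response and 100% response. SAP 6.4 tests them in a gated sequence at two-sided 0.05, which "starts with the comparison between treatment groups in the 50% response rate" once the primary has succeeded. A miss at any step stops the later key secondary tests.

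Elsewhere the SAP handles country differently:

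- The primary MMRM (6.10.1) includes it.
- The negative binomial sensitivity model (6.10.2), also fitted in GLIMMIX, includes it at first: "In case of non-convergence, country and/or baseline-by-month interaction may be excluded from the model".
- The weekly ordinal GLIMMIX model (6.10.3) includes it and states no fallback without it: "The model will include the fixed, categorical effects of treatment, country, week, and treatment-by-week interaction".
- Sustained 50% response (6.10.3) uses "logistic regression with covariate of treatment, country and continuous baseline value".
- The log-rank test for time to first 50% response (6.10.3) is stratified by country.

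For the response models, 6.10.3 already provides for failed fits. It first changes the algorithm, and then "the model will be fit using covariance matrices in the following order specified by a decreasing number of covariance parameters until convergence is met".

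**The concern.** Stratified randomisation balances country between the arms. If country predicts response, a model that ignores it does not credit that balance. Its model-based standard error is larger than the true sampling variation, and the log-odds ratio is pulled toward zero. Both effects cost power. The 50% response test is where this matters most, because missing it ends the key secondary sequence.

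The stated reason is convergence, but country has three levels (China, India, Russia in SAP 6.15) and so adds only two parameters. The other randomisation factor is covered by continuous baseline MHD, so country is the only one left out. The same 50% response outcome is analysed with country in two supportive analyses and without it in the gated test. No country-adjusted analysis of the monthly response endpoints is planned, and the country subgroup analysis covers the primary measure only. Safety models also omit country; that is not at issue here.

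**Working it through.** **1. Which tests are affected.**

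| Test, in gated order | Model | Country in model |
|---|---|---|
| Primary: monthly MHDs | MMRM | yes |
| 50% response | GLIMMIX | no |
| MSQ Role Function-Restrictive | MMRM | yes |
| 75% response | GLIMMIX | no |
| 100% response | GLIMMIX | no |

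**2. The plan's own figure.** Protocol 10.1 and SAP 5.2 give 486 patients, effect size 0.33, about 90% power and 20% discontinuation, for the primary endpoint. The normal formula gives n = 2(1.960 + 1.282)²/0.33² = 193 evaluable per arm. Then 193/0.8 gives 242 per arm, or 484 in total. With 194 per arm, t-test power is 90.0%, and 486 × 0.8 = 388.8. The design reproduces. No power is stated for the response endpoints.

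**3. Direction of the effect.** Under randomisation stratified by country, the approximate type I error of a test that ignores country is 2[1 − Φ(1.96/√(1 − R²))]. Here R² is the between-country share of the variance of the outcome tested. For R² = 5%, 1.96/√0.95 = 2.011, which gives 0.044. For R² of 1%, 3% and 10% the result is 0.049, 0.047 and 0.039. The test is conservative, never liberal.

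**4. Size for 50% response.** These inputs are assumed, because the documents give none: placebo response 40%, odds ratio 1.54, blocks of 4 within country × MHD category, and latent within-patient correlation 0.6. Dropout is monotone: 4% with no postbaseline month, 12% gone by Month 2 and 20% by Month 3. There were 10,000 simulated trials of 486 patients per cell. The model was a marginal logistic pseudo-likelihood model with the SAP's fixed effects, unstructured covariance and model-based standard errors. It was fitted to the same data with and without country. Spread is the log-odds difference between the highest and lowest country.

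| Country mix | Spread | Power without (%) | Power with (%) | Loss (points) |
|---|---|---|---|---|
| 60/20/20 | 0 | 82.1 | 82.2 | 0.1 |
| 60/20/20 | 0.5 | 81.1 | 81.5 | 0.4 |
| 60/20/20 | 1.0 (placebo 40/52/29%) | 80.0 | 81.0 | 1.0 |
| 60/20/20 | 1.5 | 77.9 | 80.7 | 2.8 |
| 60/20/20 | 2.0 (placebo 40/64/20%) | 74.5 | 79.2 | 4.7 |
| 60/20/20 | 2.5 | 71.1 | 77.9 | 6.8 |
| equal thirds | 0.5 | 80.5 | 80.9 | 0.4 |
| equal thirds | 1.0 | 78.8 | 80.6 | 1.8 |
| equal thirds | 2.0 | 67.7 | 76.3 | 8.6 |

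The Monte Carlo error of each paired difference is at most 0.33 points. Type I error without versus with country is 4.8 vs 4.9% at spread 0, 4.7 vs 5.1% at 1.0 and 3.7 vs 5.1% at 2.0. The mean log-odds ratio is 0.422 vs 0.434 at spread 1.0 (0.422/0.434 = 0.97) and 0.397 vs 0.435 at 2.0 (0.397/0.435 = 0.91). A repeat under the same assumptions gave power of 79.7 vs 81.0% at spread 1.0 and 75.8 vs 80.3% at 2.0.

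**5. 75% and 100% response.** With 5,000 trials per cell, placebo rates of 15% and 6% and odds ratios of 1.92 and 2.23, the loss is 0.3 points at spread 1.0 and about 1.5 at 2.0.

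**6. A second simulation on different assumptions.** This used 388 complete patients, country mix 50/25/25, exchangeable correlation 0.5 and 3,000 trials per cell.

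| Endpoint, placebo rates by country | Type I error, without vs with | Power (%), without vs with |
|---|---|---|
| 50%, 30% in all three | 0.047 vs 0.048 | 89.7 vs 89.8 |
| 50%, 25/35/45% | 0.043 vs 0.050 | 86.9 vs 88.3 |
| 50%, 20/40/60% | 0.024 vs 0.047 | 80.5 vs 85.8 |
| 75%, 8/15/22% | 0.046 vs 0.058 | 83.9 vs 85.9 |
| 100%, 2/5/8% | 0.041 vs 0.054 | 86.5 vs 88.2 |

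Monte Carlo standard errors are about 0.004 for type I error and 0.6 points for power. In the last two rows the adjusted test sits slightly above 0.05, so part of those power gains may not be real.

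**7. Convergence.** In the first simulation no fit failed for 50% or 75% response, with or without country. For 100% response with placebo at 6%, failures were 0% without country and at most 0.3% with it. With placebo at 2% they were 1.0–2.1% without and 2.8–14.2% with. Only the unstructured covariance was tried, so these rates apply to the first step of the SAP's sequence.

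**The case against.** The strongest reply is that the loss is close to nil on plausible inputs. At a spread of 0.5 it is 0.4 points, not far above the simulation's error bound. The larger losses need placebo response of about 20% in one country and 64% in another, and nothing in the documents supports that. Response is measured against each patient's own baseline, and baseline MHD stays in the model. Power near 80% is also assumed, and higher true power would shrink the loss. All of this stands, and it keeps the point a modest one.

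The comparison models also differ in kind. The weekly ordinal model has only a random intercept, the logistic model has one record per patient, and the negative binomial model is a sensitivity analysis. The response models estimate an unstructured covariance by pseudo-likelihood, so caution about convergence is reasonable, and for sparse 100% response it is borne out. It does not justify dropping country in advance for 50% and 75% response, where no fit failed.

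Finally, keeping country while stepping down the covariance list ranks it above unstructured covariance with Kenward-Roger degrees of freedom. Leaving the unstructured matrix brings in sandwich standard errors and between-within degrees of freedom. That ranking is a preference that the simulation did not test, although the sandwich step is already part of the SAP's sequence. A fallback that depends on the fit could also mix covariate sets along the response-distribution curve, but that curve is descriptive, with no treatment comparison.

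**Conclusion.** The concern holds as a matter of efficiency and consistency, not validity. Three of the four key secondary tests omit a factor that the trial randomises by and adjusts for in its primary analysis. Type I error is not inflated, the primary and MSQ tests are untouched, and the protocol names no covariates for the response models, so there is no departure from it. The likely loss for 50% response is 0 to 2 points of power for spreads up to 1.0. It reaches about 5 to 9 points only at spreads of 2.0 or more, and is nil if country does not predict response. These figures rest on assumed response rates, country mix, country effects and correlation, and on a stand-in for SAS GLIMMIX without Kenward-Roger. The direction is firm; the size is uncertain.

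**What to change.** Before unblinding, change SAP 6.2 so that the Study Period III GLIMMIX response models include country as a fixed main effect. Work through the algorithms and covariance structures of 6.10.3 in their listed order with country in the model. Drop country only if all of those fits fail, and report the model used for each endpoint. The baseline-by-month interaction can stay out. If one fixed mean model for all three endpoints is preferred, keep the current model and prespecify a country-adjusted sensitivity analysis instead.

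The cost is one sentence and no new data. The covariate set could differ between endpoints if the fallback is used, which in the simulation arose only for sparse 100% response. The odds ratio would become conditional on country. A fit that leaves the unstructured covariance would lose Kenward-Roger degrees of freedom, as the SAP already provides.

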6.3. Handling of Dropouts or Missing Data

Two statistical approaches to handling missing data will be used as appropriate: repeated measures analyses and ANCOVA model using change from baseline to LOCF endpoint.

For the repeated measures analyses, the model parameters are simultaneously estimated using restricted likelihood estimation incorporating all of the observed data. Estimates have been shown to be unbiased when the missing data are missing at random.

Please refer to Section 5.4.1 for approach of handling missing diary data for derivation of migraine headache days and other efficacy measures (with the exception of migraine attacks) derived from ePRO data per 30-day period.

Approaches of handling missing diary data for the derivation of migraine attack

For the derivation of the number of monthly migraine attacks, the LOCF method will be used to impute the missing ePRO diary days. If the patient was migraine headache-free on the day before the missing ePRO diary day, this would be carried forward as no migraine headache day until the actual next non-missing diary day. On the other hand, if the day before the missing ePRO diary day is a migraine headache day, then it would be carried forward as migraine headache day until the next non-missing diary day. The imputation will be carried out for all the missing diary days between the first non-missing to the last day.

If the diary compliance rate for a monthly interval is $\leq 50\%$, the number of monthly migraine attacks during that month will be considered missing. Please refer to Section 6.8 for diary compliance rate calculation.

